7.1.3. Analysis of Continuous Data

Continuous data will be summarized using descriptive statistics, including the mean, standard deviation, median, first and third quartiles, and minimum and maximum. Baseline characteristics (before and after IPTW weighting) will be compared between patients treated with warfarin and patients treated with apixaban, using the standardized difference.

7.1.4. Analysis of Categorical Data

Counts and percentages will be provided for dichotomous and polychotomous variables of baseline patient characteristics when performing descriptive analysis. Standardized difference will be calculated for each variable (before and after IPTW weighting). For calculation of standardized differences, categorical variables will be converted into a set of binary indicators, one for each non-reference level of the variable.

7.1.5. Kaplan-Meier Method

For each endpoint, Kaplan-Meier curves will be plotted for the time from the index date to first event by index OAC treatment in each of the propensity-score-weighted cohorts. The log-rank test will be used for comparison between two curves.

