3.2. STATISTICAL DECISION RULES

For primary safety and effectiveness analyses, all statistical tests will be performed at p=0.05 (twosided) with no adjustment for multiplicity. Since we will conduct various multiple subgroup analyses, which lead to the "Multiple Testing Problem". Here these subgroup analyses will be conducted with an exploratory purpose and we do not plan to conclude anything from the results here. Therefore, we will not adjust the p values and still the use p<0.05 to indicate the statistical significance.

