7.1.2. Inverse probability treatment weighting (IPTW)

IPTW with stabilized weights will be used to balance patient characteristics between two groups using propensity score calculated by using a multivariable logistic model as mentioned above (see above 7.1.2.1). However, if a treated patient has a very low propensity score, a very large weight can be created, which leads to increased variability of the estimated treatment effect. In order to address this, the weights can be stabilized by using a formula shown below, by multiplying the treatment and control weights by a constant, equal to the expected value of being in the treatment or comparison cohorts, respectively.

 $W_i = \frac{Z}{PS_i} + \frac{1-Z}{1-PS_i}$, z: probability of treatment without considering covariates

The distribution of the stabilized weight will be reviewed. If there are extreme outliers, the large weights could be set to a less extreme value (e.g. recoding all weights that are outside 5th and 95th percentile). If needed, truncation can be done after stabilizing the weights. After the weights are applied, the balance of the baseline covariates will be assessed. First, the means and proportions of baseline variables are compared. The standardized difference compares the difference in means in units of the standard deviation. If the standardized difference is less than 10%, the covariates are considered balanced.

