7.1.6. Cox proportional hazards model

Cox proportional hazards model will be used to compare endpoints (time-to-endpoint) in the propensity-score-weighted cohorts with robust sandwich estimates to account for the potential clustering within weighted sets. The Cox proportional hazards model will include only index OAC treatment as the independent variable if patient characteristics are balanced between groups... If not balanced, the unbalanced variable will be also included to the model in addition to the index OAC PFIZER CONFIDENTIAL

treatment. The hazard ratios with corresponding 95% confidence intervals and p-values will be reported.

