7.1.9. Power calculation

Incidence rates of stroke/SE and major bleeding in the primary analysis population here (that is, de novo NVAF patients initiating an anticoagulant therapy with warfarin or apixaban who have at least one bleeding risk factor) have not been investigated yet and hazard ratios of stroke/SE and major bleeding in apixaban users relative to warfarin users also have not been investigated yet. Therefore, we estimated the needed sample size to achieve adequate statistical power (e.g., 0.80) based on the major previous RCT and RWE conducted so far.

Study	Subgroup	HR	Incidence rate (%/year)	
			Warfarin	Apixaban
ARISTOTLE	-	0.79	1.60	1.27
	≥ 75 years		2.2	1.6
	≤ 60kg		3.2 2.0	
	Prior stroke or TIA		3.2 2.5	
	Diabetes		1.9	1.4
	Severe to moderate renal dysfunction		2.7	2.1
	Aspirin		1.9 1.3	
CER3		0.66	2.87	1.55

Stroke/SE

≥ 80 years	4.04	2.06
< 60 kg	3.47	2.45
Severe to moderate renal dysfunction	2.50	1.33
Anti-platelet	3.61	1.93

Major bleeding

Study	Subgroup	HR		nce rate year)
			Warfarin	Apixaban
ARISTOTLE	-	0.69	3.09	2.13
	≥ 75 years		5.2	3.3
	≤ 60kg		3.0	2.1
	Prior stroke or TIA		3.9	2.8
	Diabetes 3.1		3.1	3.0
	Severe to moderate renal dysfunction		6.4	3.2
	Aspirin		3.7	2.7
CER3		0.74	2.81	1.69
	≥ 80 years		3.94	2.35
	< 60 kg		3.67	2.61
	Severe to moderate renal dysfunction		3.32	2.21
	Anti-platelets		3.07	1.91

As shown in Tables above, absolute incidence rates of stroke/SE and major bleeding could be higher in patients with (a) risk factor(s) associated with bleeding. However, the ARISTOTLE study has revealed that P-value for interaction was mostly >0.05 and relative risk (HR) may not be changed in the specific subgroups compared to the entire cohorts

Based on the incidence rates and HRs shown above, sample size required for adequate statistical power (e.g., power=0.8) was estimated as follows,

Sample size calculation

	Assumption: Values used for calculation	Calculated results
For major bleeding		
Type I error rate	0.05	
Type II error rate	0.2	
Hazard ratio*	0.7	
N ratio in apixaban and warfarin cohorts	1:1	
Event rate for warfarin	3.77%/year**	
Event rate for apixaban	3.77%/year** 2.50%/year**	
Total events needed		246***
Estimated number of patients		7,846
	PFIZER CONFIDENTIAL	

Page 20 of 56

For Stroke/SE		
Type I error rate	0.05	
Type II error rate	0.2	
Hazard ratio*	0.7	
N ratio in apixaban and	1:1	
warfarin cohorts		
Event rate for warfarin	2.77%/year**	
Event rate for apixaban	2.77%/year** 1.79%/year**	

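### The log-rank test for the IPTW-weighted Kaplan-Meier curves is given no weighted form or robust variance, and its rank against the Cox test is not stated

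*SAP*

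**What the plan says.** - **Weights.** SAP 7.1.2: "IPTW with stabilized weights will be used to balance patient characteristics between two groups". The weight distribution is to be reviewed, and extreme weights may be pulled in, for example by "recoding all weights that are outside 5th and 95th percentile".
- **Curves.** SAP 7.1.5 plots, for each endpoint, time to first event "by index OAC treatment in each of the propensity-score-weighted cohorts". It then states: "The log-rank test will be used for comparison between two curves". No weighted version and no variance estimator is named.
- **Cox model.** SAP 7.1.6 fits a Cox model to the same weighted cohorts "with robust sandwich estimates to account for the potential clustering within weighted sets" and reports hazard ratios, 95% confidence intervals and p-values. The robust variance is stated for this model only.
- **Decision rule.** SAP 3.2: for the primary safety and effectiveness analyses, "all statistical tests will be performed at p=0.05 (twosided) with no adjustment for multiplicity". It does not name the deciding test.
- **Elsewhere.** Appendix 10.2, where further method detail could stand, is marked not applicable. The table in SAP 7.2.3 lists the Kaplan-Meier rows as plots and does not mention a log-rank test.

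**The concern.** After weighting, a patient no longer counts as one independent observation. The SAP recognises this for the Cox model but not for the log-rank test on the same data. A programmer who follows 7.1.5 literally has two obvious routes:

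1. **Leave the weights out.** The test then compares the raw apixaban and warfarin cohorts. It does not test the curves that are plotted, and it brings back the confounding that 7.1.1 and 7.1.2 are there to remove.
2. **Enter the weights as frequencies.** The test then addresses the right curves, but its variance treats a weight of 3 as three independent patients.

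At stake is the p-value attached to the curve comparison for every endpoint. For major bleeding and for stroke/SE it would be a second test at 5% beside the Cox test, with no rule for the case where the two disagree.

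**Working it through.** **1. The plan's own figures, used to set the scale.** SAP 7.1.9 assumes a hazard ratio of 0.7, two-sided 5%, power 80% and 1:1 allocation.
- Events (Schoenfeld): 4 × (1.960 + 0.842)² / (ln 0.7)² = 4 × 7.849 / 0.1272 = 246.8. The SAP states 246.
- Major bleeding, mean rate (3.77 + 2.50)/2 = 3.135%/year: 246 / 0.03135 = 7,847. The SAP states 7,846.
- Stroke/SE, mean rate (2.77 + 1.79)/2 = 2.28%/year: 246 / 0.0228 = 10,789, as stated.

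These reproduce. The fix changes none of them.

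**2. Why weights as counts go wrong.** With weight w, event indicator e, treatment A and weighted at-risk proportion p, the score is U = Σ w·e·(A − p). The frequency-weight variance is Σ w·e·p(1 − p). The robust variance sums squared contributions and so carries w². With a mean weight near 1, the z-statistic is too large by roughly √D, where D = mean(w²)/mean(w)². Type I error is then about 2 × [1 − Φ(1.96/√D)]:
- D = 1.03: 1.96/1.015 = 1.931, giving 5.3%
- D = 1.14: 1.96/1.068 = 1.836, giving 6.6%
- D = 1.36: 1.96/1.166 = 1.681, giving 9.3%
- D = 1.8: 1.96/1.342 = 1.461, giving 14.4%

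**3. Null simulation at the plan's scale.** Settings: no treatment effect; 7,846 patients; 3.135%/year; exponential censoring with mean 1.5 years, cut at the SAP's 2-year limit; estimated logistic propensity score; stabilised weights; 2,500 runs. There are three independent normal confounders, each with log hazard ratio 0.3. Their coefficient in the treatment model sets the strength of selection. The confounders, their effects, the selection strengths and the censoring pattern are assumptions, because the documents give no weight distribution. The last row used 8,000 patients, 3.1%/year and 600 runs.

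| Selection coefficient | D | Weights ignored | Stabilised weights as counts | Weighted score, robust variance |
|---|---|---|---|---|
| 0.2 | 1.03 | 29% | 4.5% | 4.0% |
| 0.4 | 1.14 | 73% | 6.8% | 4.8% |
| 0.6 | 1.36 | 94% | 10.5% | 5.4% |
| 0.8 | 1.8 | 98% | 18% | 6% |

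Monte Carlo error around a true 5% is 1.96 × √(0.05 × 0.95/2,500) = ±0.9 points for 2,500 runs and ±1.7 points for 600 runs. When the covariates had no effect on the outcome, ignoring the weights gave 4.0 to 5.2% (600 runs each). The large figures in that column are therefore confounding.

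**4. A second set of assumptions.** Settings: 6,000 patients, about 3%/year, one confounder, selection slopes 0.5, 0.8 and 1.2, risk slopes 0.5 and 0.8, 1,500 runs each.
- Weights as counts: 6.1 and 7.3% (D = 1.09), 8.7 and 9.5% (D = 1.22), 14.3 and 17.5% (D = 1.57).
- Robust: 4.8, 5.5, 4.7, 4.7, 4.9 and 6.7%.
- Weights ignored: 32% or more.

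**5. Truncation.** In one setting (coefficient 0.6, 8,000 patients, 600 runs), cutting weights at the 5th and 95th percentiles left residual confounding. The robust test rejected 12.5% of the time, against 7.2% without truncation in the same 600-run setting. A corrected log-rank variance does not cure that.

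**The case against.** The strongest reply is that the Cox model is the primary analysis and the log-rank result is only an accompaniment. Much of this stands. SAP 7.1.7 refers to the Cox model as the method of the primary analysis. The table in 7.2.3 gives Cox as the only inferential method for the primary and secondary endpoints in the balanced cohorts. SAP 2.1 lists curves, rates and hazard ratios as the comparisons, without a log-rank test. The E-values in 7.1.8 and the power calculation in 7.1.9 rest on the hazard ratio, and the protocol abstract names Cox for the treatment effect. A reader might infer that the primary result itself has an inflated type I error. The documents do not support that: the robust Cox output does not depend on the log-rank test.

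Other stronger readings also fail:
- **That an unweighted test is prespecified.** The SAP does not say so. The two curves it refers to are the weighted ones, so the sentence leans away from that reading. The 29 to 98% column shows what a literal default run could do, not what is planned.
- **That type I error is necessarily above 5%.** With little weight spread it is not (4.5% at D = 1.03). The lowest figure in the second set, 6.1%, has a Monte Carlo 95% interval of about 4.9 to 7.3%. Stabilisation, review of the weights and optional truncation all limit the spread.
- **That a wrong p-value will be printed on the figures.** No section says p-values go on the plots.

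What the reply does not answer is that 7.1.5 still prescribes a test for every endpoint, 3.2 puts all tests of the primary analyses at 5%, and no sentence says the log-rank result is descriptive or yields to Cox.

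**Conclusion.** Wrong as written, with modest impact. The test in 7.1.5 lacks the specification that weighted data need and that the next section supplies for Cox. If stabilised weights are used as counts, type I error runs from about 5% with little spread to 10 to 18% with large spread, against 4 to 7% with a robust variance. If the weights are ignored, the test answers a different, confounded question. These sizes rest on assumed selection and confounder strengths; the real weight distribution could put the study anywhere in the range, including at no material inflation. The Cox hazard ratio, confidence interval and p-value, the E-values and the sample size are unchanged. The exposure is a second p-value per endpoint that may be invalid or may conflict with Cox, with no stated rule for which one counts.

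**What to change.** Replace the log-rank sentence in SAP 7.1.5 with: *curves will be compared using the robust (sandwich) score or Wald test from the weighted Cox model in 7.1.6*. A weighted log-rank test with robust variance would also do.

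Add to SAP 3.2 that the robust weighted Cox p-value is the single deciding test for each primary endpoint. Since 7.1.6 may add unbalanced covariates to the model, say there which fitted model supplies that p-value.

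The cost is one replaced sentence and one or two added ones. The robust Cox p-value is already planned, so no new data or analysis is needed. Residual confounding from weight truncation is a separate matter that this edit does not address.

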7.1.6. Cox proportional hazards model

Cox proportional hazards model will be used to compare endpoints (time-to-endpoint) in the propensity-score-weighted cohorts with robust sandwich estimates to account for the potential clustering within weighted sets. The Cox proportional hazards model will include only index OAC treatment as the independent variable if patient characteristics are balanced between groups... If not balanced, the unbalanced variable will be also included to the model in addition to the index OAC PFIZER CONFIDENTIAL

treatment. The hazard ratios with corresponding 95% confidence intervals and p-values will be reported.

7.1.7. Exploratory subgroup analysis

For subgroup analyses, hazard ratios with 95% confident intervals (95% CI) will be calculated using the Cox proportional hazards model as in primary analysis. As mentioned above, subgroup analyses are exploratory, no definitive conclusions from these subgroup analyses would be drawn.

7.1.8. Sensitivity analysis

For the primary effectiveness and safety analysis, E-values¹⁰ (evidence for causality) will be calculated based on calculated hazard ratios and 95% confident intervals to assess the extent of unmeasured confounding. The E-value is defined as the minimum strength of association for an unmeasured confounder with both the treatment and the outcome to explain away the observed significant (if any) treatment-outcome association.

7.1.9. Power calculation

Incidence rates of stroke/SE and major bleeding in the primary analysis population here (that is, de novo NVAF patients initiating an anticoagulant therapy with warfarin or apixaban who have at least one bleeding risk factor) have not been investigated yet and hazard ratios of stroke/SE and major bleeding in apixaban users relative to warfarin users also have not been investigated yet. Therefore, we estimated the needed sample size to achieve adequate statistical power (e.g., 0.80) based on the major previous RCT and RWE conducted so far.

Study	Subgroup	HR	Incidence rate (%/year)	
			Warfarin	Apixaban
ARISTOTLE	-	0.79	1.60	1.27
	≥ 75 years		2.2	1.6
	≤ 60kg		3.2 2.0	
	Prior stroke or TIA		3.2 2.5	
	Diabetes		1.9	1.4
	Severe to moderate renal dysfunction		2.7	2.1
	Aspirin		1.9 1.3	
CER3		0.66	2.87	1.55

Stroke/SE

≥ 80 years	4.04	2.06
< 60 kg	3.47	2.45
Severe to moderate renal dysfunction	2.50	1.33
Anti-platelet	3.61	1.93

Major bleeding

Study	Subgroup	HR		nce rate year)
			Warfarin	Apixaban
ARISTOTLE	-	0.69	3.09	2.13
	≥ 75 years		5.2	3.3
	≤ 60kg		3.0	2.1
	Prior stroke or TIA		3.9	2.8
	Diabetes 3.1		3.1	3.0
	Severe to moderate renal dysfunction		6.4	3.2
	Aspirin		3.7	2.7
CER3		0.74	2.81	1.69
	≥ 80 years		3.94	2.35
	< 60 kg		3.67	2.61
	Severe to moderate renal dysfunction		3.32	2.21
	Anti-platelets		3.07	1.91

As shown in Tables above, absolute incidence rates of stroke/SE and major bleeding could be higher in patients with (a) risk factor(s) associated with bleeding. However, the ARISTOTLE study has revealed that P-value for interaction was mostly >0.05 and relative risk (HR) may not be changed in the specific subgroups compared to the entire cohorts

Based on the incidence rates and HRs shown above, sample size required for adequate statistical power (e.g., power=0.8) was estimated as follows,

Sample size calculation

	Assumption: Values used for calculation	Calculated results
For major bleeding		
Type I error rate	0.05	
Type II error rate	0.2	
Hazard ratio*	0.7	
N ratio in apixaban and warfarin cohorts	1:1	
Event rate for warfarin	3.77%/year**	
Event rate for apixaban	3.77%/year** 2.50%/year**	
Total events needed		246***
Estimated number of patients		7,846
	PFIZER CONFIDENTIAL	

Page 20 of 56

For Stroke/SE		
Type I error rate	0.05	
Type II error rate	0.2	
Hazard ratio*	0.7	
N ratio in apixaban and	1:1	
warfarin cohorts		
Event rate for warfarin	2.77%/year**	
Event rate for apixaban	2.77%/year** 1.79%/year**	
Total events needed		246***
Estimated number of patients		10,789
* estimated from ARISTOTLE and CER studies		

** averages of incidence rates shown in the Tables above

*** Calculated using an on-line calculator (Sample Size Survival Analysis (quesgen.com))

In the preliminary check to examine the feasibility of this study, we have obtained that the number of apixaban users and of warfarin users who were eligible for this study were both more than 10,000 patients. Considering that IPTW will be applied to balance the patient characteristics in this study, the number of patients eligible for this study would be adequate for the primary analysis.

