The follow-up period is variable, and will begin on the next day of the index date and continue until the earliest of the following scenarios – occurrence of target outcome event (details available in Subsection 5); discontinuation of apixaban or warfarin; switching from apixaban or warfarin; withdrawal from the database.

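### The two sample sizes in SAP 7.1.9 are person-years labelled as patients, so the adequacy statement does not demonstrate 80% power for stroke/SE

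*SAP*

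**What the plan says.** SAP 7.1.9 introduces its table by saying that the "sample size required for adequate statistical power (e.g., power=0.8) was estimated as follows". For each primary endpoint it assumes a hazard ratio of 0.7, type I error 0.05, type II error 0.2 and a 1:1 "N ratio in apixaban and warfarin cohorts". The event rates are in percent per year: 3.77 (warfarin) and 2.50 (apixaban) for major bleeding, 2.77 and 1.79 for stroke/SE. They are described as "averages of incidence rates shown in the Tables above". Each endpoint needs 246 events, and the row "Estimated number of patients" then reads 7,846 for major bleeding and 10,789 for stroke/SE.

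The section reports that more than 10,000 users of each drug were found eligible in a feasibility check. It mentions the planned IPTW and concludes that "the number of patients eligible for this study would be adequate for the primary analysis".

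SAP 2.1 states: "The follow-up period is variable, and will begin on the next day of the index date". SAP 4.1.3.1 ends follow-up at the event, discontinuation (a 45-day refill gap), a switch, withdrawal from the database, or two years. Protocol 9.5 leaves the required number of patients to the SAP, so 7.1.9 holds the study's only sizing calculation.

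**The concern.** Dividing a number of events by a rate per year gives person-years. To turn that into patients, one needs the mean time each patient is followed, and SAP 7.1.9 contains no such term. Because follow-up stops when treatment stops, the mean could fall below or above one year, and the documents do not say which.

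The adequacy sentence therefore compares two different units. It mentions IPTW without attaching a number, although SAP 7.1.2 itself recognises that very large weights make the estimated effect more variable.

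Both endpoints are primary, and under SAP 3.2 "all statistical tests will be performed at p=0.05 (twosided) with no adjustment for multiplicity". If stroke/SE shows no significant difference, this section could be cited as evidence that the comparison was adequately powered, which it does not establish.

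**Working it through.** **1. Reproducing the SAP's figures.**

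- Rates: the unweighted means of the 12 rows in each table of SAP 7.1.9 are 2.766 and 1.791 (stroke/SE) and 3.767 and 2.500 (major bleeding). These match the printed 2.77, 1.79, 3.77 and 2.50.
- Events (Schoenfeld, 1:1, two-sided 0.05, power 0.80): 4 × (1.960 + 0.842)² / (ln 0.70)² = 246.8, against the printed 246.
- Major bleeding: mean rate (3.77 + 2.50)/2 = 3.135%/year; 246/0.03135 = 7,846.9, printed as 7,846.
- Stroke/SE: mean rate (2.77 + 1.79)/2 = 2.28%/year; 246/0.0228 = 10,789.5, printed as 10,789.

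Both printed integers follow by truncation. Other candidate formulas do not return them: one-year cumulative incidence gives 7,976 and 10,919, and two-proportion formulas give 5,910 and 7,282. The printed figures are events divided by a yearly rate, summed over both cohorts.

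**2. What the label implies.** Read literally, 10,789 patients in total would give about 80% power at a mean follow-up of one year, 68% at 0.75 year and 51% at 0.5 year.

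**3. What the available patients imply.** The documented floor is 2 × 10,000 = 20,000. The mean follow-up needed to reach the SAP's own person-years, with no loss from weighting, is:

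- stroke/SE: 10,789/20,000 = 0.54 year;
- major bleeding: 7,846/20,000 = 0.39 year.

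A design effect multiplies these. At 1.2 and 1.5, stroke/SE needs 0.65 and 0.81 year, and major bleeding 0.47 and 0.59 year. Design effects of 1.2 and 1.5 correspond to effective sample sizes of 1/1.2 = 83% and 1/1.5 = 67%.

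**4. Stroke/SE power at HR 0.70.** To keep rates and hazard ratio consistent, the apixaban rate is set to 0.70 × 2.77%/year. With mean follow-up f years and design effect d:

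- effective events E = 10,000 × f × 0.0277 × (1 + 0.70) / d;
- power = Φ(√(E/4) × |ln 0.70| − 1.96).

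| Mean follow-up (assumed) | d = 1: E, power | d = 1.2: E, power | d = 1.5: E, power |
|---|---|---|---|
| 0.5 year | 235, 78% | 196, 70% | 157, 61% |
| 0.75 year | 353, 92% | 294, 86% | 235, 78% |
| 1 year | 471, 97% | 392, 94% | 314, 88% |

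**5. Sensitivity to the hazard ratio.** SAP 7.1.9 tabulates two whole-cohort stroke/SE hazard ratios: 0.66 from the previous study of this database (CER3) and 0.79 from the randomised trial. By the formula in step 1 they need 182 and about 565 events. By the formula in step 4, with the hazard ratio replaced:

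- HR 0.66: power 88% at 0.5 year without weighting loss, 82% with d = 1.2.
- HR 0.79: power 75% at one year without weighting loss, 67% with d = 1.2.

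**The case against.** The arithmetic is correct. Since the rates are per year, the label can be read as shorthand for patients followed for one year on average. On that reading 10,789 is a total over both cohorts against more than 20,000 patients, a margin of about 20,000/10,789 = 1.85. The 20,000 is itself a floor: Protocol 9.5 reports 15,902 warfarin and 22,336 apixaban patients eligible in the previous study, with data only to July 2018 and before the requirement of a bleeding risk. Stabilised weights and possible truncation (SAP 7.1.2) limit the loss from weighting. All eligible patients are used whatever the calculation says, and hazard ratios will be reported with confidence intervals, so the precision of a null result will be visible.

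Most of this stands, and it limits the consequence. It does not supply the missing one-year assumption or a figure for the weighting loss, so the adequacy sentence remains an assertion.

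Three stronger readings are tempting, and the documents support none of them.

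- **A reader might infer that the study is underpowered for stroke/SE.** That needs a short mean follow-up, a material weighting loss or a weaker effect. The documents establish none of these, and the two-year cap leaves room for a mean above one year.
- **A reader might infer that HR 0.70 is too optimistic because the randomised trial gave 0.79.** The previous study of the same database gave 0.66, so 0.70 lies between the two sources. Both belong in a sensitivity table.
- **A reader might infer that the bleeding rates are too high because the previous study's whole-cohort rates were 2.81 and 1.69%/year.** The present population is selected for bleeding risk, and the SAP explains that rates could be higher in such patients. Even at the lower rates the need is 246/0.0225 = 10,933 person-years, or 10,933/20,000 = 0.55 year per patient before any weighting loss.

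**Conclusion.** The point holds as one of unit and demonstration. That 7,846 and 10,789 are total person-years over both cohorts is certain: both reproduce exactly from the SAP's own inputs. Adequate power for stroke/SE is not demonstrated, because the mean on-treatment follow-up and the effective sample size after weighting are both unstated.

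How much this matters depends on those two quantities. At HR 0.70 and 20,000 patients, power ranges from 61% (0.5 year, design effect 1.5) to 97% (one year, no weighting loss), and every one-year case shown exceeds 80%. Major bleeding has more room, needing 0.39 year before any weighting loss. These results assume constant event rates, equal cohorts at the documented minimum, and follow-up and design effects chosen for illustration because the documents give none.

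**What to change.** In SAP 7.1.9:

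1. Relabel 7,846 and 10,789 as total person-years over both cohorts.
2. State the expected mean on-treatment follow-up and its source, and an assumed effective sample size after IPTW.
3. Give the expected events for each endpoint against the 246 required at HR 0.70. For stroke/SE add the two tabulated hazard ratios as sensitivity cases: 0.66 (182 events) and 0.79 (about 565 events).
4. Replace the adequacy sentence with the power that results.
5. Commit to reporting the achieved effective sample size per arm, (Σw)²/Σw², with the results.

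The cost is SAP wording and a short table, with no change to design, data or analysis. The stated power may look less favourable than the present sentence suggests.
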